The purpose of this study is to determine the rate of occlusion in BioFlo implanted port-catheters flushed with 20 mL of normal saline only vs those flushed with the standard practice of 20 mL of normal saline followed by 5 mL of heparinized saline (100 units per mL). The researchers also hope to conclude that the complication rate in patients whose ports are flushed with saline only is no greater than those of patients whose ports are flushed with the combination of saline and heparinized saline. These complications might include partial or complete obstruction, infection of the central line, and/or the onset of heparin induced thrombocytopenia.

Research Question(s):

1. Does a saline only flush maintain the patency of BioFlo Port at a rate comparable to a heparinized saline solution?
2. Is there any difference in the type and rate of complications among BioFlo Ports flushed with saline only versus heparinized saline?

Null Hypothesis:

We are proposing a non-inferiority trial. Thus, the null hypothesis is: BioFlo Ports flushed with saline only will experience an occlusion rate of more than 10% over the occlusion rate experienced in implanted port catheters flushed with a heparinized saline solution.

The alternative hypothesis is: BioFlo Ports flushed with saline only will experience an occlusion rate less than 10% over the occlusion rate experienced in implanted port catheters flushed with heparinized saline solution.

Background Information/Literature Review:

Currently at TriHealth, Inc. all implanted port catheters are flushed according to the TriHealth Nursing Policy and Procedure Intravenous Site Guidelines (See Appendix A). An implanted port catheter is flushed with 20 mL of normal saline after IV medication, blood, or blood draws. Heparinized saline in the amount of 5 mL (concentration 100 units/mL) is used as a final flush

when no IV fluids are running and before de-accessing. This is intended to maintain patency of the catheter until the next use.

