During FY 2012, 391 patients with implanted port catheters were treated in the OPCC. Seventy of these patients experienced an occlusion of their port that required the administration of alteplase (CathFlo) ([name], personal communication, October 12, 2012). Thus, 70 of 391 experienced an occlusion resulting in an occlusion rate of 18%. Some of these 70 patients experienced an occlusion more than once during that time. Additionally, during that time, a few patients had their implanted port catheters removed due to infection or malfunction. The exact number of patients who experienced multiple occlusions or had their implanted ports removed/replaced during FY2012 is unknown.

During the planning of the current study evaluating implanted port catheters, we engaged the consultation of a biostatistician through the Center for Clinical and Translational Science and Training (CCTST) to conduct a power analysis to

establish the number of participants needed in each group to determine the non-inferiority of the alternative therapy (saline only flush). Consultation was provided by [name], Associate [name] Hospital Medical Center, University of Cincinnati.

Based on the literature and our own experience we estimated an approximate occlusion rate of 20% with the standard treatment (saline + heparinized saline flush as described above). The power analysis conducted by [name] determined that, using a two group normal approximation test of proportions with a one-sided .05 significance level, a sample size of 198 participants per group will have 80% power to reject the null hypothesis that the proposed method is not inferior (i.e. the difference in proportions between the proposed method and the standard method is greater than 0.10). Thus, we will continue to recruit participants in that study until 198 have been enrolled in each group for a total of 396 study participants.

[name] was consulted again when the introduction of the BioFlo Port at TriHealth was discovered. It is [name] recommendation that this second randomized controlled trial using the same methodology and power analysis calculations be conducted. Thus, we will recruit 198 participants per group for a total of 396 participants in this study.

Data Collection:

Independent Variables: Method for flushing implanted port catheters:

- 20 mL of saline followed by 5 mL of Heparinized saline in a concentration of 100 units/mL
OR
- 20 mL of saline only

Dependent Variables:

Primary Outcomes

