- Occurrence of first complete (can neither withdraw blood nor flush the catheter) occlusion
- Occurrence of first partial (able to flush but unable to withdraw blood) occlusion
- Frequency with which alteplase (CathFlo) has to be utilized to resolve an occlusion

Secondary Outcomes

- Number of subsequent occurrences of complete or partial occlusions after the first occurrence.
- Amount of time in days that a port remains patent (flushes easily and able to obtain a blood return).
 - Amount of time between entrance in study and first incidence of partial or complete occlusion

- Amount of time between incidences of partial or complete occlusion.
- Occurrence of other complications:
 - Central Line-Associated Blood Stream Infection (CLABSI) – a laboratory-confirmed (recognized pathogen cultured from one or more blood cultures; organism cultured from blood is not related to an infection at another site) blood stream infection that is considered central line associated (CDC, 2012).
 - Develops complication related to Heparin
 - HIT (Heparin induced thrombocytopenia as measured by a positive HIT antibody test)
 - Other heparin allergy

Moderating variables: other things that could also affect patency of the port

- Number of times port flushed per month or frequency of flushing.
- Use of prophylactic doses of anticoagulant drugs (e.g., enoxaparin, heparin, warfarin)
- Development of a hypercoaguable state, as diagnosed by primary hematologist/oncologist
- Mechanical difficulties related to port placement e.g. “Pinch-off syndrome”
- Length of time port has been in place prior to entrance in study

Extraneous variables:

- Type of cancer
- Age of participant

Data collection tool

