The data collection tool (see Implanted Port Catheter Flushing Data Collection Form – Face Sheet: Appendix C and Record of Flushes: Appendix D) were developed by the principal and sub-investigators specifically for the purpose of this study. The tool was reviewed by the OPCC nurses for completeness and clarity. In addition to basic demographic information (age, gender), the nurse will record the patient's type of cancer, and the diagnosis or history of any hypercoaguable state or use of anticoagulant medication as documented in the patient chart. The nurse will also document the type of implanted port catheter (single/double), the port location (right/left, subclavian vein (described in the operative note or chest x-ray), and the date the port was inserted so that length of time the port has been in place can be calculated. Data will be recorded on the Face Sheet when the patient is enrolled in the study and as pertinent information/events become known, i.e., as complications occur.

With each visit to the identified treatment center, the nurse will document the date and characteristics related to the patency of the port catheter on

the Record of Flushes data collection tool. In the event the blood withdrawal is sluggish or absent, the patient will receive a dose of alteplase (CathFlo) according to the TriHealth Nursing Policy: VAD: Care & Maintenance (Appendix A) and as ordered by the physician. Dosage and results of that intervention will also be recorded on the Record of Flushes data collection tool. In the event that any study participant (regardless of group assignment) requires alteplase (CathFlo) on three (3) consecutive visits to the treatment center, the patient's participation in the study will be terminated and they will be excluded from further data collection. The patient will be returned to a standard maintenance protocol for flushing of the port as prescribed by the afore-mentioned TriHealth Nursing policy (see Appendix A) or as prescribed by attending physician.

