Participants in the control group will have yellow colored data collection Face Sheets while participants in the intervention group will have blue colored data collection Face Sheets. The Record of Flushes sheet will be white for patients in both groups. A blue or yellow sticker will be placed on the cover of the patient folder housed in treatment center noting the patient's involvement in the study. The data collection Face Sheet and the current Record of Flushes sheet will be kept in the individual patient folder as long as they remain a participant in the study. As the Record of Flushes data sheet becomes full, they will be collected by study staff and placed in locked drawer in a TriHealth office.

Experimental Aspect of the Study:

Patients who agree to participate in this study will be randomized to either the control group or intervention group as explained above.

Participants in the control group will have their implanted port catheters flushed according to the established TriHealth Nursing Policy: Venous Access Devices (VAD): Care and Maintenance (see Appendix A). Following the use of the port catheter with no continuous fluids running, or before de-accessing a port catheter (removing the port needle), the port will be flushed with 20 ml of normal saline and 5 ml of heparinized saline in the concentration of 100 units of heparin per mL.

Participants in the intervention group will have their ports flushed with normal saline only. That is, following the use of the port catheter with no continuous fluids running, or before de-accessing a port catheter (removing the port needle), the port will be flushed with 20 ml of normal saline. Turbulent flushing technique (the solution is injected using a push/pause technique every 1 mL) will be used in both groups and all accessed port catheters will have a neutral displacement connector. The MicroCLAVE® Clear displacement connector (ICU Medical, Inc., San Clemente, CA, USA) is the current product in use. Participants in both groups will be seen in a TriHealth Cancer Institute Infusion Center at a frequency consistent with their individual treatment plan and as outlined in the TriHealth

Nursing Policy: Venous Access Devices (VAD): Care and Maintenance (see Appendix A). Participants will remain in the study for 12 months or until they experience one of the potential risks noted below. Participants will be considered as having completed the study if they participate for 12 months.

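### The three listed primary outcomes do not include the single per-patient occlusion proportion for which the 0.10 margin and 198 per group were set, and no rule says which outcome decides

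*Combined protocol and SAP*

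**What the plan says.** All references are to the combined protocol and SAP.

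- **Null Hypothesis.** One hypothesis on one undifferentiated rate: "BioFlo Ports flushed with saline only will experience an occlusion rate of more than 10% over the occlusion rate" seen with heparinized saline.
- **Recruitment (power analysis).** The calculation uses a single proportion: "we estimated an approximate occlusion rate of 20% with the standard treatment". With a difference of 0.10, one-sided 0.05 and 80% power, it gives 198 per group. The historical support is 70 of 391 patients, or 18%: "Seventy of these patients experienced an occlusion of their port that required the administration of alteplase (CathFlo". Complete and partial occlusions are not separated there, and each patient counts once.
- **Primary Outcomes.** Three entries: first complete occlusion; "Occurrence of first partial (able to flush but unable to withdraw blood) occlusion"; and "Frequency with which alteplase (CathFlo) has to be utilized to resolve an occlusion". None has its own expected rate or margin. The third does not say whether patients treated or doses are counted.
- **Secondary Outcomes.** Only here does the outcome list join the two types, for example "Amount of time between entrance in study and first incidence of partial or complete occlusion".
- **Statistical Analysis.** Generic two-group tests apply to all dependent variables. No deciding endpoint is named, and no rule says whether one or all primaries must succeed.

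**The concern.** Following the listed primaries as written does not test the hypothesis that was powered. The powered quantity, the proportion of participants with any occlusion, is not among them. Two competent analysts could each test a different outcome against 0.10 and both claim to follow the plan, so the deciding outcome could be settled after the data are seen.

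The outcomes are not interchangeable. An absolute margin of 0.10 on a 20% event tolerates a rise to 30%. On a rarer component the same 0.10 tolerates a much larger relative increase. If alteplase use is counted in doses, a margin on a difference in proportions cannot be applied to it at all. The study's stated aim is to change flushing policy, so the verdict should rest on an outcome fixed in advance.

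**Working it through.** **Inputs from the plan (Recruitment):** control rate 0.20, margin 0.10, one-sided alpha 0.05 (z = 1.645), power 80% (z = 0.842), 198 per group. The saline rate is not stated and is taken as equal to control. **Assumed, because the documents give no figure:** the split of occlusions into complete and partial.

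**1. Reproduce the sample size.** n = (z_alpha + z_beta)² × 2p(1 − p) / margin². With unrounded z values this is 6.1826 × 2 × 0.20 × 0.80 / 0.01 = 197.8, so 198. The plan's figure is right for one binary endpoint at 20%. Planning rate: 70/391 = 17.9%.

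**2. What the margin tolerates.** At 20%: 0.30/0.20 = 1.5-fold. At an assumed 5%: 0.15/0.05 = 3-fold.

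**3. Chance of passing when saline is truly 10 points worse on any occlusion.** Pass rule: observed difference + 1.645 × SE < 0.10, with SE from the unpooled variance and 198 per group. The normal approximation is Φ[(0.10 − true difference)/SE − 1.645]. Rates are control against saline, and the illustrative split has no participant with both types (5% + 15% = 20%; 10% + 20% = 30%).

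| Outcome tested | True rates | SE | Approximation | Exact enumeration |
|---|---|---|---|---|
| Any occlusion | 20% vs 30% | √[(0.16 + 0.21)/198] = 0.0432 | Φ(0 − 1.645) = 0.050 | 0.050 |
| Complete only | 5% vs 10% | √[(0.0475 + 0.09)/198] = 0.0264 | Φ(1.897 − 1.645) = 0.60 | 0.608 |
| Partial only | 15% vs 20% | √[(0.1275 + 0.16)/198] = 0.0381 | Φ(1.312 − 1.645) = 0.37 | 0.371 |

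Each component differs by only 5 points here, so it lies inside the margin on its own while the total sits at the margin.

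**4. Power of the pooled outcome at 198 per group with no true difference (exact enumeration).** 15%: 0.874. 18%: 0.827. 20%: 0.800. 25%: 0.744. At 25%, the formula in step 1 gives 6.1826 × 2 × 0.25 × 0.75 / 0.01 = 231.8, so 232 per group for 80% power.

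**The case against.** The strongest reply is that any occlusion is plainly meant. There is one hypothesis on one rate. The historical count takes patients with at least one occlusion and does not separate types. The Statistical Analysis section speaks of the occurrence and rate of occlusion without distinguishing type, and no section attaches the margin to a component. This stands as evidence of intent and makes the problem a missing link rather than two rival rules. It does not close the gap, because the composite is absent from the primary list. The planning count also points partly elsewhere: it is a count of patients whose occlusion needed alteplase, which is close to the third primary if that is read as patients treated.

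A second reply is that the pass probabilities depend on an invented split. That is correct, and they show direction only.

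A reader might infer something stronger: that success on any one primary is enough, so the trial carries a grossly inflated false-success rate. The plan states no such rule, and any figure for it would depend mainly on the assumed split and overlap. If all three had to pass, with alteplase counted as patients treated for either type, false success could not exceed the pooled test's 5%, because that test would be one of the three. Nor do the documents support reading this as a sample-size error: 198 reproduces.

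Two neighbouring points should not add weight here.

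- Alteplase is also given when withdrawal is sluggish (Data collection tool), which is wider than the two occlusion definitions. How such a port counts may be settled in Appendices A and D, which were not available.
- Experimental Aspect of the Study is inconsistent on when participation ends, but a first-occlusion composite is unaffected by whether a participant stays in after the first event.

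**Conclusion.** The point holds as a mismatch between the powered hypothesis and the listed primary outcomes, with no decision rule to bridge them. It should be corrected, and it does not undermine the sample size.

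The mismatch rests on the text alone. Its size cannot be fixed from the documents. Under one assumed split, a saline arm truly at the margin on any occlusion would pass 61% of the time on complete occlusion alone and 37% on partial alone, against 5% on the pooled outcome. Other splits and overlaps would give other figures. No claim is made that the plan permits success on a single component; it simply does not say.

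**What to change.** By a dated amendment made before outcomes are compared by group:

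1. Name one primary: first partial or complete occlusion, yes or no per participant, within 12 months, tested against the 0.10 margin at one-sided 0.05.
2. Make complete occlusion, partial occlusion and alteplase use secondary, with confidence intervals. State whether alteplase is counted as patients treated or doses.
3. Add a sensitivity analysis counting every alteplase-treated port as an event, because the 18% planning rate was a count of alteplase-treated occlusions.
4. State that 198 per group gives 80% power at a 20% rate, with the values in step 4 of the working for other rates.

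Separately, reconcile the text in Experimental Aspect of the Study on when participation ends. One sentence reads "Participants will remain in the study for 12 months or until they experience one of the potential risks noted below", and the risks then listed include partial occlusion. The following text ends participation for occlusion only after three consecutive occluded visits or port removal. Secondary Outcomes also counts occlusions after the first.

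**Cost.** No extra participants if the endpoint's rate is 20% or lower; about 232 per group at 25%. The protocol is dated June 2017 and the planned start was about February 2016, so enrolment may be under way. Group assignment is visible on folder stickers, and alteplase use by group is reviewed monthly. The amendment therefore needs IRB review and a record of which by-group information had been seen. **Downside.** The components are no longer each confirmatory, and the composite may be narrower than the planning event if that count included ports treated for sluggish withdrawal.

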Potential risks for study participants in either arm of the study include partial occlusion (can instill flush solution but not withdraw blood) and complete occlusion (can neither instill flush solution nor withdraw blood). Study participants could require removal of the port if an occlusion cannot be resolved, and possibly require re-insertion of a new implanted port. In the event of any occlusion, alteplase (CathFlo) in the policy established dose and frequency (see Appendix A) will be instilled to resolve the occlusion. Study participants whose implanted ports are found occluded on three (3) consecutive visits to the treatment center will be excluded from further data collection, i.e., their participation in the study will be terminated. The standard flushing as prescribed by the TriHealth Nursing Policy (see Appendix A) or as prescribed by the attending physician will be used. Study participants whose occlusion cannot be resolved with alteplase and require removal of the port will also be terminated and excluded from further data collection. Patients who develop port infections necessitating port removal will be terminated and excluded from further data collection. Study participants who develop HIT (heparin induced thrombocytopenia) or other heparin allergy will be terminated and excluded from further data collection. Likewise, patients who have thrombotic or embolic phenomenon requiring therapeutic anticoagulation will be terminated and excluded from further data collection.

The study will be closed if there is evidence that study participants in the intervention arm experience implanted port occlusion at a disproportionate rate. The amount of alteplase (CathFlo) used in each group will be assessed each month for monitoring purposes.

The undertaking of this research does require the participation of other personnel, facilities or departments other than those used in data collection. In the event the study participant is admitted to the hospital or requires some intervention using their implanted port catheter (e.g., CT scan with contrast), the study participant will have an information card describing his/her participation in the study and the group to which he/she has been randomized, so that the assigned flush solution is used, and integrity of the study can be maintained. The study participant will receive the card with instructions at the time of his/her enrollment in the study (see Appendix E Wallet Study Card).

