Statistical Analysis: Descriptive statistics will be used to describe the participants. Differences between groups on the dependent variables will be calculated using t-test, Chi-Square or Fisher's exact test as appropriate for the level of data under analysis (also see discussion regarding interim analysis). Regression analysis will be used to determine the effect of the moderating variables on the occurrence of occlusion in the implanted ports. Participants in the

control group and intervention group will be further stratified based on frequency of port flushing. Differences in the rate of occlusion between stratified groups will also be calculated.

Ethical Considerations: The purpose of this study is to determine the safest and most effective flushing solution(s) for maintaining patency in implanted port catheters. In so doing, study participants could be placed at potential risk for catheter occlusion. All catheter occlusion will be treated according to TriHealth policy, i.e., the instillation of alteplase (CathFlo) (see Appendix A). Potential study participants will be made aware of the risk when enrolled in the study (See Appendix B) script for recruiting patients into the study and the Informed Consent Statement).

Informed Consent: Patients who meet inclusion criteria will be approached by a member of the research team who will explain the study, implications of their participation and review the Informed Consent Statement and HIPAA Authorization Forms (see the attached). One signed copy of the Informed Consent Form and HIPAA forms will be given to the study participant and another placed in their folder in the TriHealth Infusion Center to be scanned into their EPIC electronic health record (EHR). The original signed Informed Consent Statement and HIPAA will be stored in a locked drawer in a TriHealth office until the study is completed and closed with the IRB. The RN seeking consent and PI will document the informed consent process in the participant's EHR. Additionally, the blue or yellow sticker on the patient folder in the treatment center and presence of data collection forms in the patient folder will indicate that the patient is a participant in the study.

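### Alteplase frequency is a primary outcome with no unit or exposure denominator, and none of the named tests allows for the unequal observation time that the protocol builds in

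*Combined protocol and SAP*

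**What the plan says.** Under Dependent Variables, Primary Outcomes, the third item is "Frequency with which alteplase (CathFlo) has to be utilized to resolve an occlusion". It has no unit, window or denominator.

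Statistical Analysis gives one general sentence: "Differences between groups on the dependent variables will be calculated using t-test, Chi-Square or Fisher's exact test as appropriate for the level of data". It assigns no test to this outcome and mentions no rate, offset or censoring. The regression and the stratification by flushing frequency in the same section concern occlusion, not alteplase use.

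Observation time is unequal by design. Experimental Aspect of the Study states: "Participants will remain in the study for 12 months or until they experience one of the potential risks noted below". The paragraph on risks that follows opens: "Potential risks for study participants in either arm of the study include partial occlusion (can instill flush solution but not withdraw blood) and complete occlusion". It then lists exits that end data collection, among them:
- "Patients who develop port infections necessitating port removal will be terminated and excluded from further data collection"
- "patients who have thrombotic or embolic phenomenon requiring therapeutic anticoagulation will be terminated and excluded from further data collection"
- HIT or another heparin allergy
- port removal for an occlusion that alteplase does not resolve.

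Data collection tool adds a rule that depends on the outcome itself, for a participant who "requires alteplase (CathFlo) on three (3) consecutive visits to the treatment center, the patient's participation in the study will be terminated".

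**The concern.** An alteplase use can be recorded only while a participant is under data collection. In a plain count, or in a yes/no for ever treated, a port watched for one month without a use scores the same as a port watched for twelve. The arm comparison then mixes how often alteplase is needed with how long each arm was watched.

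This is a primary outcome in a trial meant to support a change of flushing practice. If saline participants leave earlier, part of a real excess of alteplase use on saline could go unseen. If heparin participants leave earlier, an excess on saline could be exaggerated. If the denominator is left open, it can also be chosen after the results are known.

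**Working it through.** **The plan's own figure.** The power paragraph (under Recruitment) gives 198 per group for 20% in both arms, margin 0.10, one-sided 0.05 and 80% power. Unpooled normal approximation: n = 2 × 0.16 × (1.645 + 0.842)² / 0.10² = 197.84, rounded up to 198. It reproduces. It concerns the occlusion proportion only; no calculation or margin exists for alteplase.

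**Effect of lost time on mean counts.** Assumptions, none from the documents: true rates of 0.30 (heparin) and 0.45 (saline) uses per year; a fraction e leaves at times uniform over 12 months, unrelated to the outcome. The mean observed fraction is 1 − e/2, and the mean count is rate × (1 − e/2).

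| Exit, heparin | Exit, saline | Mean count, heparin | Mean count, saline | Difference | Ratio |
|---|---|---|---|---|---|
| 0% | 0% | 0.3000 | 0.4500 | 0.1500 | 1.50 |
| 5% | 5% | 0.2925 | 0.4388 | 0.1463 (−2.5%) | 1.50 |
| 10% | 10% | 0.2850 | 0.4275 | 0.1425 (−5%) | 1.50 |
| 20% | 20% | 0.2700 | 0.4050 | 0.1350 (−10%) | 1.50 |
| 40% | 40% | 0.2400 | 0.3600 | 0.1200 (−20%) | 1.50 |
| 5% | 10% | 0.2925 | 0.4275 | 0.1350 (−10%) | 1.46 |
| 10% | 5% | 0.2850 | 0.4388 | 0.1538 (+2.5%) | 1.54 |
| 20% | 40% | 0.2700 | 0.3600 | 0.0900 (−40%) | 1.33 |
| 40% | 20% | 0.2400 | 0.4050 | 0.1650 (+10%) | 1.69 |

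Dividing each mean count by its observed fraction returns 0.30 and 0.45 in every row, because exit was assumed unrelated to the outcome.

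**Rates tied to the protocol's figures.** If 20% and 30% have at least one use by 12 months at constant rates, the rates are −ln(0.8) = 0.223 and −ln(0.7) = 0.357 per year: difference 0.134, ratio 1.60. With mean follow-up of 10 months (heparin) and 8 (saline), the counts are 0.186 and 0.238: difference 0.052, ratio 1.28. With 8 and 10 months they are 0.149 and 0.297: difference 0.148, ratio 2.00.

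**Visit-level simulation.** Assumptions: 17 visits in 12 months; per-visit probabilities 1.65% and 3.0%, varying between patients; a 30% or 50% chance of a repeat at the next visit.
- *Equal dropout of 30% or 50% by month 12 (30% repeat):* the count difference falls from 0.289 to 0.240 or 0.204 (−17%, −29%), with the ratio at about 1.80. The rate per observed time restores 0.288 to 0.289. The difference in proportion ever treated falls from 0.314 − 0.186 = 0.128 to 0.269 − 0.158 = 0.111, or to 0.235 − 0.137 = 0.098.
- *Three-consecutive-visit stop, 30% repeat:* true difference 0.289, count 0.269, rate per observed time 0.275.
- *Same stop, 50% repeat:* true difference 0.374, count 0.305, rate 0.326. The ratio is 1.79 true, 1.75 by count and 1.79 by rate.
- *Early HIT exits in 1% to 5% of the heparin arm only, equal true rates* (the incidence quoted in Background Information/Literature Review): saline looks worse by about 0.004 to 0.016 uses, ratio 1.01 to 1.05.
- *Exit at first occlusion (30% repeat):* counts cannot exceed one; difference 0.125, mean follow-up 10.8 months (heparin) and 9.9 (saline).

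**Sections side by side.** The follow-up sentence in Experimental Aspect of the Study, read with the risk paragraph it points to, would end participation at a first occlusion. The three-visit rule, and the secondary outcomes that count and time later occlusions, require participation to continue. Until these agree, it is unclear whether more than one use per participant can be counted.

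**The case against.** The strongest reply is that the plan is merely brief. It never says that raw counts will be compared: frequency could mean a count, a proportion or a rate, and a t-test can be run on per-participant rates. Eligibility also selects patients with treatment projected for at least three months and 12 months of expected care. The only figures bearing on exit are HIT in 1% to 5% of those exposed to heparin, and a few ports removed for infection or malfunction among 391 patients in FY 2012. At exits of 5% to 10%, equal across arms, the difference shrinks by only 2.5% to 5%.

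Much of this stands. A reader might infer that counts will be compared outright, or that follow-up runs from a few days upward; the documents state neither. A reader might also infer that the distortion always favors saline, or moves the result toward non-inferiority. It does not. Equal exit leaves the ratio of means alone, heparin-related exits act against saline, and the margin belongs to the occlusion rate only. Nor do the documents support the 40% shrinkage, which needs exits of 20% against 40%.

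The gap remains. A count or an ever-treated proportion ignores time. An unweighted t-test on individual rates gives a participant with one use in one month a rate of 12 per year, with the same weight as a full year of follow-up. If a rate was intended, the plan must say so.

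**Conclusion.** The point holds as a defect of definition and analysis. A primary outcome lacks a denominator, observation time varies by design, and no test as named accounts for it.

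The size cannot be fixed from the documents. Under uniform exit unrelated to the outcome, equal exits of 5% to 40% shrink the absolute difference by 2.5% to 20% and leave the ratio of mean counts unchanged. With unequal exits, an assumed true ratio of 1.50 reads anywhere from 1.33 to 1.69 in the scenarios shown, according to which arm loses more time. The direction is therefore open.

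An offset deals with exit unrelated to the outcome. For the three-visit stop it recovers the difference only in part (0.326 against 0.374 with 50% repeat, although closer than the count's 0.305). The sample size of 198 per group is unaffected.

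**What to change.** In Statistical Analysis, define the outcome as alteplase uses per participant over time under observation. Analyse it by negative binomial (or robust Poisson) regression on arm, with offset log(days from enrolment to last recorded visit or termination). Report uses per 100 port-months by arm and the rate ratio with its confidence interval. Give uses per accessed visit as a supporting analysis, since visit frequency follows individual treatment plans.

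Report follow-up time and reasons for exit by arm. Add a sensitivity analysis for termination that depends on the outcome: the three-consecutive-visit stop and port removal for unresolved occlusion. The offset's incomplete correction of these exits is the downside and should be stated.

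Reconcile Data collection tool and Experimental Aspect of the Study on whether a single occlusion ends participation.

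The cost is a few sentences and a standard model. Visit dates and alteplase results are already recorded, and a secondary outcome already needs the entry date. Two checks remain: the protocol text does not mention a recorded termination date, and it describes recording only at treatment-center visits, so uses during hospital admissions may be missed.
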